9.2. Rituximab

9.2.1. Description

Rituximab (Rituxan®, MabThera®) is a genetically engineered chimeric murine/human monoclonal IgG1 kappa antibody directed against the CD20 antigen found on pre-B and mature B cells (Genentech 2016). Rituximab is produced by mammalian Chinese hamster ovary cells. The protein has an approximate molecular weight of 145 kD.

The drug is provided as a clear, colorless, preservative-free liquid concentrate containing 10 mg/mL of rituximab. The product is formulated in 9 mg/mL sodium chloride, 7.35 mg/mL sodium citrate dihydrate, 0.7 mg/mL polysorbate 80, and water for injection with a pH of 6.5.

9.2.2. Packaging

Rituximab is supplied in 100-mg (10-mL) or 500-mg (50-mL) single-use vials.

9.2.3. Source

Unless otherwise instructed by the sponsor, the rituximab to be used in this study may be obtained from available commercial supplies.

9.2.4. Storage and Stability

Rituximab vials are stable at 2°C-8°C (36°F-46°F). Vials should be protected from direct sunlight and should not be frozen or shaken.

Diluted rituximab solutions for infusion may be stored at $2^{\circ}C-8^{\circ}C$ ($36^{\circ}F-46^{\circ}F$) for 24 hours and are known to be stable for an additional 24 hours at room temperature. However, since rituximab solutions do not contain a preservative, diluted solutions should be stored refrigerated ($2^{\circ}C-8^{\circ}C$).

No incompatibilities between rituximab and polyvinylchloride or polyethylene bags have been observed.

Version 9, 18 Feb 2020

9.2.6. Solution Preparation

Before use, the rituximab vials should be inspected for particulate matter or discoloration. Any vial with evidence of particulates or discoloration should not be used.

Using aseptic technique, the necessary amount of rituximab should be withdrawn from the vial and diluted to a final concentration of 1 to 4 mg/mL in an infusion bag containing either 0.9% Sodium Chloride, USP or 5% Dextrose in Water, USP. The bag should be gently inverted to mix the solution. The infusion solution should not be mixed or diluted with other drugs. Any unused portion of rituximab remaining in the vial should be discarded.

9.2.7. Accountability

Acquisition, storage, control, and disposal of rituximab used in the study should be performed according to institutional procedures and policies.

The investigator and/or the responsible site personnel must maintain accurate records of the source, dates of administration, quantities of administration, and lot numbers of the rituximab dispensed for this study.

9.3. Atezolizumab

9.3.1. Description

Atezolizumab (TECENTRIQ®) is an Fc-engineered, humanized, monoclonal antibody that binds to PD-L1 and blocks interactions with the PD-1 and B7.1 receptors (Genentech 2017). Atezolizumab is a non-glycosylated IgG1 kappa immunoglobulin that has a calculated molecular mass of 145 kDa.

The drug is provided as a sterile, preservative-free, colorless to slightly yellow solution in single-dose vials. Each mL of TECENTRIQ contains 60 mg of atezolizumab and is formulated in glacial acetic acid (16.5 mg), L-histidine (62 mg), sucrose (821.6 mg), polysorbate 20 (8 mg). The solution has a pH of 5.8.

9.3.2. Packaging

Atezolizumab is supplied in a carton containing one 1200-mg/20-mL single-dose vial.

9.3.3. Source

The atezolizumab to be used in this study will be supplied by Genentech, Inc. via the study sponsor (LAM Therapeutics, Inc.).

9.3.4. Storage and Stability

Atezolizumab vials are stable at 2°C-8°C (36°F-46°F). Vials should be stored in the original cartons protected from light and should not be frozen or shaken.

Atezolizumab does not contain a preservative; thus, diluted solutions should be administered as soon as possible after preparation. If the diluted atezolizumab solution is not used immediately, it may be stored or maintained at room temperature (e.g., $20^{\circ}\text{C}-25^{\circ}\text{C}$; $68^{\circ}\text{F}-77^{\circ}\text{F}$). for ≤ 6 hours from the time of preparation, including time for administration of the infusion. Alternatively, it may be stored under refrigeration at $2^{\circ}\text{C}-8^{\circ}\text{C}$ ($36^{\circ}\text{F}-46^{\circ}\text{F}$) for ≤ 24 hours.

Version 9, 18 Feb 2020

9.3.5. Solution Preparation

Before use, the atezolizumab vials should be inspected for particulate matter or discoloration. Any vial with evidence of particulates or discoloration should not be used. The vial should not be shaken.

Using aseptic technique, 20 mL of atezolizumab should be withdrawn from the vial and diluted into a 250-mL polyvinyl chloride, polyethylene, or polyolefin infusion bag containing 0.9% Sodium Chloride Injection, USP. The bag should be gently inverted to mix the solution. Shaking of the bag must be avoided. The infusion solution should not be mixed or diluted with other drugs. Used or empty vials of atezolizumab should be discarded.

The intravenous solution should be prepared and dispensed by the study center pharmacist and should be infused by a qualified nurse with experience in monitoring the administration of chemotherapeutic agents.

9.3.6 Accountability

Acquisition, storage, control, and disposal of atezolizumab used in the study should be performed according to institutional procedures and policies.

The investigator and/or the responsible site personnel must maintain accurate records of the source, dates of administration, quantities of administration, and lot numbers of the atezolizumab dispensed for this study.

Section 10.1.1.4 Adverse Event of Special Interest

Change: A definition of adverse events of special interest has now been added.

Adverse events of special interest (AESIs) comprise TLS occurring in any study subject. Among study subjects receiving atezolizumab the following treatment-emergent AEs will be considered AESIs:

- AE suggestive of hypersensitivity, infusion-related reactions, cytokine-release syndrome, influenza-like illness, systemic inflammatory response syndrome, or systemic immune activation
- Autoimmune hemolytic anemia
- Cardiac disorders Grade ≥ 2 : atrial fibrillation, myocarditis, pericarditis
- Colitis
- Cutaneous reactions: Stevens-Johnson syndrome, bullous dermatitis, toxic epidermal necrolysis
- Drug-induced liver injury (Grade ≥ 3 serum ALT or AST increase in combination with a Grade ≥ 2 serum total bilirubin)
- Endocrinopathy: diabetes mellitus, pancreatitis, adrenal insufficiency, hyperthyroidism, or hypophysitis
- Hepatitis (Grade ≥3 serum ALT or AST increase)

Version 9, 18 Feb 2020

- Muscular disorders: myositis, myopathy, rhabdomyolysis
- Nephritis
- Neurological disorders: Guillain-Barre syndrome, myasthenic syndrome or myasthenia gravis, or meningoencephalitis
- Ocular toxicities: uveitis, retinitis, optic neuritis
- Pneumonitis
- Systemic lupus erythematosus
- Transmission of an infectious agent due to contamination of atezolizumab
- Vasculitis

AESIs will be described in narratives as indicated in Section 10.6.

Section 10.6 SAE and AESI Reporting

Change: Reporting requirements for SAEs have been updated and reporting requirements for AESIs have now been added.

The investigator is obligated to immediately report to **Pharmalex Data Safety Solutions**, Inc. (DSS) each SAE and each AESI that occurs during this investigation, within 24 hours from knowledge of the event, whether or not it is considered study-drug related. All requested supplementary documents (e.g., discharge summary, autopsy report) and relevant data (e.g., ECGs, laboratory tests, discharge summaries, post mortem results) must be faxed or emailed within 24 hours to DSS at the contact below:

• FAX to email a copy to

The information provided in a SAE or AESI report to DSS should be as complete as possible, but contain a minimum of the following:

- A short description of the AE (diagnosis) and the reason why the AE was categorized as serious an SAE or AESI
- Subject identification and treatment
- Investigator's name and telephone number (if applicable)
- Name of the suspect medicinal product and dates of administration
- Assessment of causality.

If any questions or considerations regarding SAE or AESI report requirements or report completion arise, the principal investigator/site staff should contact DSS-PharmaLex. Medically related questions or concerns regarding treatment should be directed to the sponsor's medical monitor.

If all information about the SAE or AESI is not yet known, the investigator will be required to report any additional information within 24 hours as it becomes available. SAEs and AESIs

Version 9, 18 Feb 2020

must be followed and reported upon until the event has completely resolved to Grade 0 or baseline or until the event becomes a new stable baseline condition for a subject.

All SAEs and AESIs will be evaluated by the sponsor's medical monitor or designee.

The investigators must notify their governing IRB of any SAEs in accordance with Section 18.1.

For any suspected adverse reaction that is both serious and unexpected (not documented in the IB or package insert), an Investigational New Drug (IND) safety report or revision to the IB may be issued to inform all investigators involved in any study with LAM-002A.

Section 11. ASSESSMENT OF EFFICACY

Changes: References to the schedules of assessment tables were included to clarify where information regarding the timing of efficacy assessments could be found.

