Dose escalation decisions will be evaluated in a DLT-evaluable population. The DLT-evaluable population will include subjects who complete Cycle 1 dosing or who are withdrawn from study due to a DLT in Cycle 1. A subject will be deemed non-evaluable for determining DLTs and will not be counted toward the total cohort size if the subject did not experience a DLT, did not receive at least 75% (42/56 BID schedule; 63/84 TID schedule, 18/24 intermittent schedule) of the planned first-cycle doses or discontinued from the study prior to completing necessary safety evaluations through the first 28 days of study treatment. These subjects may be replaced unless accrual to the cohort has stopped due to DLT.

Section 6.7. Definition of LAM-002A Dose-Limiting Toxicity (DLT)

Change: Information regarding DLT definitions was moved to this section (previously in Section 6.7.2.5) to provide an easier flow of concepts. No changes to the substance of the DLT definitions were made except that the inability to administer the required minimum number of doses on the intermittent schedule due to drug-related AEs was added as a necessary new DLT criterion.

A DLT will be defined as an AE or abnormal laboratory value meeting the criteria in Table 3 and that is assessed as unrelated to disease, a comorbid condition, intercurrent illness, or concomitant medications (see Table 4). For the purposes of dose escalation and determination of the LAM-002A MTDs, DLTs that occur within the first cycle of treatment must be included in decisions regarding dose escalation. DLTs or other clinically significant toxicities that occur after Cycle 1 may also be considered when determining the RP2D.

Version 9, 18 Feb 2020

Table 4: Criteria for Defining Dose-Limiting Toxicities (DLTs)

Toxicity	Criteria
Hematology	CTCAE Grade 4 neutropenia lasting ≥ 7 days CTCAE Grade 4 febrile neutropenia CTCAE Grade 3 thrombocytopenia with bleeding that requires transfusion therapy CTCAE Grade 4 thrombocytopenia
Toxicity	Criteria
Gastrointestinal	≥ CTCAE Grade 3 vomiting or nausea despite the use of optimal anti-emetic treatments ≥ CTCAE Grade 3 diarrhea despite the use of optimal anti-diarrheal treatments
Renal	Serum creatinine > 3.0 x ULN
Hepatica	Total bilirubin \geq CTCAE Grade 3 Total bilirubin \geq CTCAE Grade 2 and ALT or AST \geq CTCAE Grade 2 or, for subjects with liver metastases at baseline, total bilirubin \geq 2.0 x ULN and ALT or AST \geq CTCAE Grade 3

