Pneumonitis	Interrupt for Grade 2; resume when Grade ≤ 1	Grade ≥3	For Grade ≥2, corticosteroids, 1-2 mg/kg of prednisone equivalents
Hepatitis	Interrupt for Grade 2 elevations of serum AST or ALT (> 3-5 x ULN) or total bilirubin (> 1.5-3 x ULN); resume when Grade ≤ 1	Grade ≥3 elevations of serum AST or ALT (> 5 x ULN) or total bilirubin (> 3 x ULN)	For Grade ≥2, corticosteroids, 1-2 mg/kg of prednisone equivalents
Colitis	Interrupt for Grade 2 or 3; resume if Grade ≤ 1 within 12 weeks on ≤ 10 mg oral prednisone equivalents	Grade 4	For Grade 2 recurrent or persistent (> 5 days), corticosteroids, 1-2 mg/kg of prednisone equivalents; For Grade ≥3, methylprednisolone 1-2 mg/kg intravenous → oral corticosteroid taper over ≥ 1 month

Pancreatitis	Interrupt for Grade 2 or 3 pancreatitis or Grade ≥3 increases in serum amylase or lipase levels (>2 x ULN); resume if Grade ≤ 1 within 12 weeks on ≤ 10 mg oral prednisone equivalents	Grade 4 pancreatitis or any grade of recurrent pancreatitis	For Grade ≥2, methylprednisolone 1-2 mg/kg intravenous → oral corticosteroid taper over ≥ 1 month
Hypophysitis	Interrupt for symptoms; resume when Grade ≤ 1	-	Administer corticosteroids and hormone replacement as clinically indicated
Thyroid disorders	Interrupt for symptoms; resume when Grade ≤ 1		For symptomatic hypo- or hyperthyroidism, initiate hormone replacement or anti- thyroid drug, as needed
Adrenal insufficiency	Interrupt for symptoms; resume if Grade ≤ 1 within 12 weeks on ≤ 10 mg oral prednisone equivalents		For symptoms, methylprednisolone 1-2 mg/kg intravenous → oral corticosteroid taper over ≥ 1 month
Diabetes mellitus	Interrupt for Grade ≥3 hyperglycemia (serum glucose ≥ 250 mg/dL; resume when blood sugar control achieved		Insulin for Type 1 diabetes mellitus
Meningitis, encephalitis, myasthenic syndrome, myasthenia gravis, or Guillain- Barré syndrome		Any grade	Methylprednisolone 1-2 mg/kg intravenous → oral corticosteroid taper over ≥ 1 month
Rash	Interrupt for Grade 3; resume when Grade ≤ 1	Grade 4	For Grade 2, topical corticosteroids. For Grade ≥ 3, corticosteroids, 1-2 mg/kg of prednisone equivalents

Version 9, 18 Feb 2020

Infection	Grade 3 or 4; resume when control of infection achieved	_	Treat with appropriate systemic antibiotics for suspected or confirmed infections
-----------	---	---	---

Abbreviations: ALT=alanine aminotransferase, AST=aspirate aminotransferase, ULN=upper limits of normal

Section 6.9 Other Supportive Care Recommendations

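### The drug-induced liver injury AESI sits wholly inside the hepatitis AESI, so non-serious ALT/AST Grade 2 with bilirubin Grade 2 or higher gets no expedited report or narrative in atezolizumab subjects

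*Combined protocol and SAP*

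**What the plan says.** Section 10.1.1.4, added by Amendment 6, names tumor lysis syndrome as an AESI for every subject. It then adds a list for one group only: "Among study subjects receiving atezolizumab the following treatment-emergent AEs will be considered AESIs". Two entries in that list concern the liver:

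- "Drug-induced liver injury (Grade ≥ 3 serum ALT or AST increase in combination with a Grade ≥ 2 serum total bilirubin"
- "Hepatitis (Grade ≥3 serum ALT or AST increase"

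Section 10.1.1.4 also calls for narratives of AESIs. Section 10.6 requires each SAE and each AESI to be reported "within 24 hours from knowledge of the event, whether or not it is considered study-drug related", followed until resolved or stable, and evaluated by the medical monitor.

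Two other parts of the plan set liver thresholds.

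- **Table 4 (Section 6.7, dose-limiting toxicities).** One hepatic criterion is "Total bilirubin \geq CTCAE Grade 2 and ALT or AST \geq CTCAE Grade 2". For subjects with liver metastases at baseline the criterion is instead bilirubin at or above 2.0 x ULN with ALT or AST Grade 3 or higher. Bilirubin Grade 3 or higher is also dose-limiting by itself.
- **Table 6 (Section 6.8.4.4, atezolizumab modifications), hepatitis row.** "Interrupt for Grade 2 elevations of serum AST or ALT (> 3-5 x ULN) or total bilirubin (> 1.5-3 x ULN". Grade 3 or higher elevation of either (transaminase above 5 x ULN or bilirubin above 3 x ULN) leads to permanent discontinuation of atezolizumab.

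**The concern.** The two liver entries share the same transaminase threshold, and the injury entry only adds a further condition to it. A narrower entry beside a broader one cannot bring in a new event. Bilirubin therefore has no influence on whether a liver event in an atezolizumab subject is an AESI.

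This leaves a gap where the plan elsewhere treats the finding as important. Take a subject on LAM-002A plus atezolizumab with ALT 4 x ULN and bilirubin 2.5 x ULN. By the Table 6 limits both are Grade 2. The subject meets the Table 6 interruption trigger twice over and, without baseline liver metastases, meets the laboratory thresholds of the Table 4 pair. If the event is not serious, it is not expedited to the sponsor and gets no AESI narrative.

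Prompt notice has some value here. Section 6.1.3 enrolls the first 3 subjects in each combination cohort one at a time, with at least 3 weeks of observation between them, and each atezolizumab cohort has only 6 planned subjects.

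**Working it through.** The plan gives no figure to reproduce. The check compares sets of laboratory grades.

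**Inputs.** Let T be the ALT/AST grade (0 to 4) and B the total bilirubin grade (0 to 4), which gives 5 x 5 = 25 combinations. The parentheses in Section 10.1.1.4 are read as complete definitions.

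| Set | Source | Condition | Count |
|---|---|---|---|
| Injury AESI | 10.1.1.4 | T ≥ 3 and B ≥ 2 | 2 x 3 = 6 |
| Hepatitis AESI | 10.1.1.4 | T ≥ 3, any B | 2 x 5 = 10 |
| Hepatic pair, no liver metastases | Table 4 | T ≥ 2 and B ≥ 2 | 3 x 3 = 9 |

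**Step 1: does the injury entry add anything?** Injury minus hepatitis is empty, and the union is 10, the same as hepatitis alone. Hepatitis minus injury is T = 3 or 4 with B = 0 or 1, which is 4 combinations. The injury entry is therefore a strict subset.

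**Step 2: which Table 4 pairs are not AESIs?** The pair minus the union leaves T = 2 with B = 2, 3 or 4: 3 of the 9 combinations. By the Table 6 limits this is ALT/AST above 3 and up to 5 x ULN with bilirubin above 1.5 x ULN.

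**Step 3: what does the plan do with those three?**

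| T, B | Table 6 (atezolizumab) | Table 4, no liver metastases | AESI |
|---|---|---|---|
| 2, 2 | Interrupt | Dose-limiting through the pair only | No |
| 2, 3 | Permanently discontinue | Dose-limiting through the pair, and through bilirubin alone | No |
| 2, 4 | Permanently discontinue | Dose-limiting through the pair, and through bilirubin alone | No |

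**Step 4: effect of aligning the entry with the pair.** With T ≥ 2 and B ≥ 2 the injury entry adds 3 combinations beyond hepatitis. AESI coverage goes from 10 to 13 of 25, and the pair combinations missed go from 3 to 0.

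**Step 5: subjects with liver metastases at baseline.** Their Table 4 criterion already needs T ≥ 3, which lies inside the hepatitis entry. Keeping that criterion adds no report for them, so the gain is confined to subjects without liver metastases.

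**Population.** Table 2 plans 6 evaluable subjects in each of cohorts 7 and 8, so 6 + 6 = 12.

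**The case against.** The strongest reply is that nothing is lost through the overlap itself: every event meeting the injury entry is already reported as hepatitis, and the entry still labels a more severe subgroup. That is right. The loss lies in the events outside both entries.

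A second reply is that Table 4 serves another purpose. Section 6.7 says that "DLTs that occur within the first cycle of treatment must be included in decisions regarding dose escalation", whereas the liver AESIs concern atezolizumab subjects in Stage 2. No text requires a dose-limiting threshold and a reporting threshold to agree, so a reader who infers that the plan contradicts itself goes further than the documents allow. The reply does not dispose of the point, however. Table 6 applies directly to atezolizumab subjects. Section 6.8.2.5 also uses LAM-002A-related dose-limiting toxicities to trigger dose modification without limiting this to Stage 1.

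Third, a reader might infer that mixed liver injury goes unnoticed or unmanaged. The documents do not support that. Adverse events are recorded throughout, chemistry is drawn on Days 1, 8 and 15 of Cycle 1 and Day 1 of later cycles (Table 11), Table 6 prescribes action, and serious cases are reported within 24 hours. Discontinuations for adverse events also feed the boundaries in Section 14.1.2.

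Fourth, it is tempting to say that a combined entry exists in order to catch lower transaminase rises. The documents state no such purpose, and the point does not need it.

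Finally, 3 of 9 is a count of grade combinations. It is not an event rate and gives no measure of how much would be under-reported.

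**Conclusion.** The point holds and is minor. The bilirubin condition in Section 10.1.1.4 never makes an event reportable. Non-serious, treatment-emergent ALT/AST Grade 2 with bilirubin Grade 2 or higher in atezolizumab subjects gets no 24-hour AESI report, AESI follow-up or narrative, although Table 6 acts on it and Table 4 counts it as dose-limiting outside baseline liver metastases.

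The size is 3 grade combinations, of which only Grade 2 with Grade 2 depends on the pair rather than on bilirubin alone, among about 12 planned subjects. At Version 9 the prospective effect is smaller. The extension stage expects fewer than 4 subjects, and its data collection is limited to SAE reports, although the amended Section 10.6 still refers to AESIs. For the completed stages, the definition still determines which cases receive AESI narratives.

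The conclusion rests on these assumptions:

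- The Amendment 6 wording of Sections 10.1.1.4 and 6.7 is still in force. The later changes shown do not alter it, but the current body text is in the part not available, as is the footnote to the hepatic row of Table 4.
- Some such events would be non-serious. The SAE definition is not in the available part, so their share cannot be estimated.
- Dose-limiting status also requires the event to be assessed as unrelated to disease, a comorbid condition, intercurrent illness or concomitant medications.

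**What to change.** Change the drug-induced liver injury entry in Section 10.1.1.4 to match the full hepatic pair in Table 4: treatment-emergent ALT or AST Grade 2 or higher with total bilirubin Grade 2 or higher; for subjects with liver metastases at baseline, bilirubin at or above 2.0 x ULN with ALT or AST Grade 3 or higher. Leave the hepatitis entry unchanged.

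The liver-metastases criterion should be carried over. Section 7.1 admits ALT/AST up to 5 x ULN with liver involvement, which reaches the Grade 2 range of Table 6, and bilirubin up to 3 x ULN in Gilbert disease. The entry should therefore say expressly that the abnormality is treatment-emergent, so that a baseline value alone does not qualify.

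This changes a reporting threshold only and leaves every treatment rule as it is. It costs one line in the protocol and the same line in any safety plan, and possibly a few more 24-hour reports and narratives among at most about 12 planned subjects. No new tests are needed, because ALT, AST and total bilirubin are already in the Table 11 chemistry panel. If the protocol is not amended again, the same definition can be applied when selecting narratives for the study report.

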11. ASSESSMENT OF EFFICACY

Tumor response will be assessed in the Dose Escalation Stage and Expansion Stage using modified Lugano Response Criteria for NHL (Cheson 2014) and revised guidelines for the diagnosis and treatment of CLL (Hallek 2008, Cheson 2012) (see Appendix 2).

Pretreatment tumor assessments will be performed within 30 days of the first dose (bone marrow assessment may be performed within 2 months prior to first dose) and will include diagnostic CT scans (with intravenous contract) or PET/CT for subjects with lymphoma (CT only for subjects with CLL/SLL), bone marrow aspirate/biopsy, complete blood counts and physical examination. It is anticipated that in most cases the PET and CT scans will be conducted using a single instrument, i.e., as a PET/CT scan (CT scans should be performed using a contiguous reconstruction algorithm of ≤ 5 mm). However, MRI is an acceptable alternative method for assessing disease in subjects who cannot receive intravenous contrast with CT scans. In such subjects MRI and PET scans will have to be obtained separately. Baseline bone marrow biopsies/aspirates may be omitted if not deemed essential for response assessment or patient management.

During treatment, radiology studies will be performed for tumor assessments within 7 days prior to Day 1 of Cycles 3, 5, 7 and then every 3 months thereafter as indicated in Table 8: Schedule of Assessments (LAM-002A Continuous Monotherapy Administration), Table 9: Schedule of Assessments (LAM-002A Intermittent Monotherapy Administration), Table 10: Schedule of Assessments (LAM-002A/Rituximab Combination Therapy), and Table 11: Schedule of Assessments (LAM-002A/Atezolizumab Combination Therapy) in Section 8.7. until PD or use of alternative antineoplastic therapy. If necessary per applicable response criteria, a repeat bone marrow biopsy or aspirate will be required for subjects who have a Complete Response (CR) by imaging and physical examination. Subjects with CLL/SLL who achieve CR will require assessment of minimal residual disease (MRD) by flow cytometry of bone marrow and peripheral blood.

Protocol: LAM-002A-NHL-CLN01

Version 9, 18 Feb 2020

Section 12. PHARMACOKINETIC ASSESSMENTS

Changes: Additional information regarding the timing of pharmacokinetic assessments was provided, and references to the schedules of assessment tables were included to clarify where information regarding the timing of pharmacokinetic assessments can be found. Collection of unscheduled pharmacokinetic samples was removed because it is difficult to manage and provided little incremental information over the frequent pharmacokinetic samples that were already planned.

